Participants will continue to receive palovarotene until it is reimbursed in the country where the study is being conducted, or another access programme becomes available, or until the study end date of November 2024 is reached, whichever occurs first. At this time, investigational palovarotene will be discontinued to allow participants to transition to the commercially available drug, physician-prescribed palovarotene, or to another access programme, if available. Early access can only take place if it is allowed within the local laws, rules and regulations or specifically approved in writing by local authorities.

Participants can voluntarily withdraw from the study at any time for any reason.

The study intervention can be discontinued for individual participants by the investigator if he/she believes the participants' safety is at risk.

In the event of early study withdrawal or early discontinuation of the study intervention, all reasonable efforts should be made by the study personnel in-clinic or remotely to have the participants complete all study assessments of the EW Visit as per the SoA.

Participants will be followed-up in-clinic or remotely for safety for 30 days after the last palovarotene dose of the study is received. If the study intervention was discontinued due to a safety concern, the participant will be monitored for safety (see [Section 8.3.3](#) for follow-up of AEs/serious adverse events (SAEs) and [Section 8.3.5](#) for follow-up of pregnancies).

The EOS for an individual participant will be the date of study completion due to palovarotene becoming reimbursed in the country where the study is being conducted, or another access programme becoming available, or the study end date of November 2024 being reached, whichever occurs first.

The maximum duration of the study is three years from enrolment to last study visit (November 2021 to November 2024).

An Independent Data Monitoring Committee (IDMC) will be set-up, as described in [Section 10.1.5](#).

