## 2.2 Overall Study Design and Investigational Plan

Study CLIN-60120-452 is a multicentre, noncomparative rollover study with the aim of continuing to provide palovarotene to participants with FOP who have completed one of the

parent studies (Study PVO-1A-301 or PVO 1A 202/PVO 1A 204) and, in the investigator's judgement, may benefit from palovarotene therapy. Participants who have completed the parent study are defined as those who have completed the parent End of Study (EOS) or End of Treatment Visit.

[figure not shown]
The study is designed primarily to further evaluate the safety of palovarotene and secondly, to collect efficacy data in male and female participants aged  $\geq 14$  years (qualifying as skeletally mature or, based on investigator's assessment, have reached final adult height) with FOP treated with palovarotene.

Participants are eligible for the study whether they are receiving chronic or flare-up treatment in the parent study at the time of transition. Participants who previously interrupted/stopped palovarotene treatment and are currently under parent study follow-up due to the premature physeal closure (PPC) related partial clinical hold in participants  $<14$  years, are eligible for the study if they are  $\geq 14$  years of age and skeletally mature/have reached final adult height based on investigator's assessment. There must be a current parent study signed informed consent (ICF) form for the participant to be eligible for Study CLIN-60120-452.

A maximum of 87 participants from studies PVO-1A-301, PVO-1A-202/PVO-1A-204 are eligible to be enrolled and will receive palovarotene once daily at the dose received during their participation in the parent study at the time of transition to Study CLIN-60120-452 or prior to interrupting/stopping palovarotene treatment.

The study will consist of an Inclusion Visit (Day 1) (which ideally corresponds to the parent EOS Visit), a continuous dosing treatment period (including a Follow-up Visit every six months), and an EOS/Early Withdrawal (EW) Visit. The maximum duration is three years from enrolment to last study visit (November 2021 to November 2024). The study schema is below:

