**Chronic treatment:** oral palovarotene once daily, 5 mg, or at the dose received during participation in the parent study at the time of transition Study CLIN-60120-452 or prior to interrupting/stopping palovarotene treatment.

**Flare-up treatment:** increase in dose at the time of a flare-up (or substantial high risk traumatic event likely to lead to a flare-up) to 20 mg once daily for 4 weeks (28 days), followed by 10 mg once daily for 8 weeks (56 days) for a total of 12 weeks (84 days) even if symptoms resolve earlier.

Participants receiving flare-up treatment at the time of transition to Study CLIN-60120-452 will continue and complete the flare-up treatment as was planned in the parent study.

Flare-up treatment should begin at the onset of the first symptom indicative of a FOP flare-up or substantial high risk traumatic event likely to lead to a flare-up. Chronic treatment should cease at the time of initiation of flare-up treatment, re-initiation of the chronic daily treatment should occur after completion of the flare-up treatment.

**Persistent flare-up symptoms:** treatment may be extended in 4-week intervals with 10 mg palovarotene and continued until the flare-up symptoms resolve.

**Intercurrent flare-up:** if the participant experiences an intercurrent flare-up (new flare-up location or marked worsening of the original flare-up) at any time during the flare-up treatment, then the 12-week flare-up treatment should be restarted.

In the case of any intolerable adverse reactions, the daily dose of the chronic/flare-up regimen can be reduced.

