### 5.7.2.2 Primary Analysis – Adverse Events

All adverse events (AEs) recorded in the eCRF will be coded using the latest version of MedDRA dictionary at the time of the database lock and will be classified by System Organ Class (SOC) and Preferred Term (PT). [Note: All ongoing AEs at the time of participant transition will be transferred from the parent study database]

AEs will be classified as Treatment-Emergent AEs (TEAEs) according to the rules below:

- Events with start date on or after the date of first IMP administration and up to 30 days after date of last dose of treatment of palovarotene in Study CLIN-60120-452 (or date of last contact if not available).

- Ongoing AEs from the parent study with a worsening in intensity or relationship (see relationship and intensity order below) to the study intervention following transition to Study CLIN-60120-452. New AEs during Study CLIN-60120-452 will be compared by SOC and PT to all previous study ongoing AEs for comparison of the intensity and relationship.

Ongoing AEs from the parent study with no change in intensity or relationship to the study intervention following transition to Study CLIN-60120-452 will therefore be an AE (non-TEAE).

In the case where it is not possible to define an AE as treatment emergent or not, the AE will be classified by the most conservative case; i.e. treatment emergent.

The below summaries will be provided:

- An overview table summarising the:
  - number and percentage of participants with at least one of the following AEs: any AE; any TEAE; maximum intensity of TEAEs; causality of TEAEs, worst causality and intensity of TEAEs (worst case); TEAE leading to a dose change; TEAE leading to withdrawal; TEAE leading to death; Serious Adverse Events (SAEs); Serious TEAE;
  - corresponding number of events for each of the AE categories listed above
- A summary of the number and percentage of participants reporting an AE by SOC and PT
- A summary of the number and percentage of participants reporting a TEAE by SOC and PT
- A summary of the number and percentage of participants reporting a TEAE by maximum intensity, SOC and PT
- A summary of the number and percentage of participants reporting a TEAE by worst causality, SOC and PT
- A summary of the number and percentage of participants reporting a related TEAE by SOC and PT
- A summary of the number and percentage of participants reporting a TEAE by intensity, causality, SOC and PT

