- A summary of the number and percentage of participants reporting a non-Serious TEAE by SOC and PT
- A summary of the number and percentage of participants reporting a non-Serious related TEAE by SOC and PT
- A summary of the number and percentage of participants reporting a TEAE leading to treatment discontinuation by SOC and PT
- A summary of the number and percentage of participants reporting a TEAE leading to dose change (increase or decrease) by SOC and PT

The below summaries will also be provided by treatment dose at time of AE onset (5mg, 10/20mg and all palovarotene):

- Overall summary of Adverse events
- A summary of the number and percentage of participants reporting a TEAE by SOC and PT

- A summary of the number and percentage of participants reporting a TEAE by maximum intensity, SOC and PT
- A summary of the number and percentage of participants reporting a TEAE by worst causality, SOC and PT
- A summary of the number and percentage of participants reporting a TEAE leading to treatment discontinuation by SOC and PT
- A summary of the number and percentage of participants reporting a TEAE leading to dose change (increase or decrease) by SOC and PT

To calculate the treatment regimen at time of AE onset, the start date of each AE will be merged with each participant dosing log. Given dosing end dates are not captured the latest dosing record prior to the AE start date will be identified. If the dosing record is either 0 mg or after treatment discontinuation the regimen will be set to “off treatment”.

AEs will be counted as follows:

- AEs summaries will be ordered in terms of decreasing frequency for SOC and PT within the overall column of each output.
- Participants with more than one AE within a particular SOC are counted only once for that SOC. Similarly, participants with more than one AE within a particular PT are counted only once for that PT.
- Participants reporting a TEAE more than once within that SOC/ PT, the TEAE with the worst-case intensity (intensity order: severe > missing > moderate > mild) will be used in the corresponding intensity summaries.
- Participants reporting a TEAE more than once within that SOC/ PT, the TEAE with the worst-case causality to study medication (order: related > missing > not related) will be used in the corresponding relationship summaries;

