### **Deaths and SAEs**

The below summaries will be provided:

- A summary of the number and percentage of participants reporting a serious TEAE
- A summary of the number and percentage of participants reporting a serious related TEAE
- A summary of the number and percentage of participants reporting a TEAE leading to death
- A summary of the number and percentage of participants reporting a serious TEAE by treatment dose at AE onset (5mg, 10/20mg and all palovarotene)

The below listings will be also provided:

- All SAEs

- All TEAEs leading to treatment discontinuation
- All Deaths

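### TEAE tables by dose at onset give participant percentages without time at risk, so their columns mix event rate with time spent at each dose

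*SAP*

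**What the plan says.** SAP 5.7.2.2 first plans TEAE tables overall and by treatment regimen, then adds a second set: "The below summaries will also be provided by treatment dose at time of AE onset (5mg, 10/20mg and all palovarotene"). That set contains an overall AE summary and five tables by SOC and PT. The Deaths and SAEs part adds a table of participants "reporting a serious TEAE by treatment dose at AE onset".

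Apart from the overall summary, each table is a number and percentage of participants, counted once per SOC or PT. The main overview table also gives the "corresponding number of events for each of the AE categories listed above". No AE table mentions person-time or a rate. The SAP does use time-based measures elsewhere: annualised healthcare use (5.7.3.5) and a flare-up rate from a Poisson model with a time offset (5.7.3.7).

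On allocating events, the SAP says "To calculate the treatment regimen at time of AE onset, the start date of each AE will be merged with each participant dosing log", taking the latest dosing record before onset. It continues: "If the dosing record is either 0 mg or after treatment discontinuation the regimen will be set to" an off-treatment value. No column is listed for that value. Appendix A4 gives n as the percentage denominator, with a footnote if needed.

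On time at each dose, SAP 2.2 sets a flare-up course "for a total of 12 weeks (84 days) even if symptoms resolve earlier", with extension or restart possible. It also says "The maximum duration is three years from enrolment to last study visit". Individual follow-up varies by design; Protocol 4.1 says "Participants will continue to receive palovarotene until it is reimbursed in the country where the study is being conducted", or until one of two other end conditions is met.

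**The concern.** The percentage of participants with at least one event grows with time at risk. Many of the same people can contribute to both dose columns, for very different lengths of time. A reader who compares the two columns cannot tell a difference in rate from a difference in duration.

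Safety is the primary objective, and the dose contrast is of real interest: Protocol 2.2.3 reports that mucocutaneous AEs leading to dose reduction were more common during 20/10 mg treatment than during chronic treatment. The regimen columns classify participants. Only the dose-at-onset tables separate events within participants who received both kinds of dosing. If those tables can hide, reverse or exaggerate a rate difference, they do not do the job they were added for.

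**Working it through.** **Inputs from the documents.** One course is 28 + 56 = 84 days, which agrees with the total in SAP 2.2. Maximum duration is three years (SAP 2.2). At most 87 participants can enrol (SAP 2.3).

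**Assumptions.** The documents give no AE rate, number of courses or follow-up distribution. The figures below assume constant rates within each kind of dosing and unextended courses. AE rates are illustrative.

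**Step 1: break-even ratio.** With a constant rate, P(at least one event) = 1 − exp(−rate × time). Two columns for the same participants are equal when rate × time is equal. For follow-up of T days and c courses, the break-even ratio (flare-up rate over chronic rate) is (T − 84c) / (84c). It needs no assumed AE rate and applies equally to expected event counts.

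| Follow-up | Courses | Calculation | Break-even ratio |
|---|---|---|---|
| 1 year | 1 | 281/84 | 3.35 |
| 2 years | 1 | 646/84 | 7.7 |
| 3 years | 1 | 1011/84 | 12.0 |
| 2 years | 3 | 478/252 | 1.90 |
| 1 year | 2 | 197/168 | 1.17 |
| 1 year | 3 | 113/252 | 0.45 |

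Below the break-even ratio the flare-up column is the lower one. In the last row it is higher even when the true rates are equal.

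**Step 2: illustration over 730 days, assumed rates 0.5 per year chronic and 1.0 per year flare-up.**
- One course: chronic 1 − exp(−0.5 × 646/365.25) = 58.7%; flare-up 1 − exp(−1.0 × 84/365.25) = 20.5%. Expected events per 100 participants are 50 × 646/365.25 = 88 and 100 × 84/365.25 = 23.
- Two courses: 53.7% versus 36.9%. Three courses: 48.0% versus 49.8%.
- Equal rates of 0.5 per year, one course: 58.7% versus 10.9%, a gap due to time alone.
- Reverse case, one year, three courses, equal rates of 0.1 per year: 3.0% versus 6.7%.

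**Step 3: denominator.** If half the participants have one course, the 20.5% above becomes about 10.3% when divided by the whole FAS instead of those ever on flare-up dosing. The SAP text does not say which applies.

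**Step 4: can a reader rebuild the rates?** Only roughly. The duration summaries in SAP 5.8.2 are not linked to AE counts, and two formulas do not suit this use:
- 5.8.2 ends the last period at the last dose date when collected, but 5.8.2.1 takes last contact as the last dose date.
- 5.8.2.3 subtracts all flare-up days from the span between first and last chronic dose, even flare-up days before the first chronic dose. For a participant who enters on an 84-day course and then has 646 chronic days, it gives 646 − 84 = 562 days, which is 84/646 = 13% too low.

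**Step 5: precision of the added rates.** If all 87 participants have one course, flare-up time is 87 × 84/365.25 = 20.0 person-years. Twenty events give 100 per 100 person-years (exact Poisson 95% CI 61 to 154). Two events of one PT give 10 (1.2 to 36).

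**The case against.** **The study is descriptive.** The endpoint is incidence of TEAEs, nothing is tested, and the protocol does not ask for dose-at-onset tables. This stands. A reader might infer that the primary analysis is invalid. It is not: the Overall column is a proper crude incidence.

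**Other planned output already helps.** A reader might infer that only the dose-at-onset tables separate flare-up from chronic dosing. They do not: all summary tables are split into chronic only, flare-up only, and both. What remains is the group that received both. The dose-at-onset overall summary probably carries event counts, so with the duration summaries a rough rate by hand may be possible, within the limits of step 4.

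**The break-even ratios need constant risk.** This is the strongest objection. If events cluster after a dose change, percentages do not track time and rates can mislead. Suppose a 20% chance of one event after starting each kind of dosing, over two years with one course. The percentages are 20% and 20%, but the rates are about 11 (0.20/1.77) and 87 (0.20/0.23) per 100 person-years. Rates should therefore sit beside the percentages, not replace them.

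**The direction is not fixed.** A reader might infer that the tables must understate flare-up risk. Extended, restarted or frequent courses shrink or reverse the effect.

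**Regimen columns.** A reader might also infer serious bias there. The effect is small and uncertain. In simulations with assumed rates (AEs 0.3 per year in everyone, flare-ups 0.5 to 2 per year), gaps ran from 0 to 16 points depending on the spread of follow-up, and were about 1 to 2 points if everyone had two to three years. All lie within the sampling interval of about ±20 points for 87 participants split evenly.

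**Layout may be settled elsewhere.** SAP 1 refers to separate table shells, which may define denominators and columns. They are not available here.

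**Conclusion.** The point holds as a limit on how the dose-at-onset tables can be read. Their percentages mix event rate with duration, and the documents' own 84-day course and three-year maximum allow those durations to differ greatly within one person. Under constant rates and one course each, a flare-up rate up to 3.35, 7.7 or 12.0 times the chronic rate (1, 2 or 3 years) would still not show as a higher percentage. With three courses in one year the distortion runs the other way.

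The mechanism is clear from the text. Confidence in the magnitude is only medium, because course frequency, follow-up and the shape of the risk over time are unknown. Person-time would also not make the contrast causal: Protocol 8.1.7 has bone growth and loss of mobility after a flare-up reported as AEs, so flare-up rates stay confounded by indication. This is a low-cost improvement and ranks below changes the plan should not go without.

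**What to change.** In SAP 5.7.2.2, keep the planned percentages and amend the dose-at-onset tables as follows.

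- **Rates.** Show person-years per column and add events per 100 person-years with 95% CIs. Use the Poisson offset approach of 5.7.3.7 with robust variance for the any-TEAE and any-serious-TEAE rows, and exact Poisson intervals for sparse SOC and PT rows. If participants with an event per 100 person-years are also shown, stop each person's time at the first event.
- **Allocation.** Assign events and time by type of dosing record: chronic, flare-up or off treatment. The 5 mg and 10/20 mg labels do not say where reduced doses belong (Protocol 6.5, Table 5 lists 15, 12.5, 7.5, 2.5 and 1 mg among others). State each column's percentage denominator as participants ever exposed in that category.
- **Time.** Build on-treatment time from the dosing periods in 5.8.2, ending at the last dose date when collected, not from the summed durations in 5.8.2.1 and 5.8.2.3. Count as off treatment the 0 mg periods and the time from last dose to 30 days later or last contact, whichever is earlier. This matches the TEAE window, so late events have time at risk.
- **Footnote.** Say that the rates assume roughly constant risk within a dosing category, that flare-up rates are confounded by indication, and that the columns are not comparative.

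The cost is SAP wording, programming and more output. Dosing start dates are already collected and the periods already derived. The main downside is imprecision, as step 5 shows.

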### 5.1.4 *Reference Start Date and Study Day*

Reference start date is defined as the day of the first IMP administration of palovarotene (Day 1) in Study CLIN-60120-452. Study day will be calculated as:

- The difference between the event date and the reference date plus one day, if the event is on or after the reference date.
- The difference between the event date and the reference date, if the date of event is prior to the reference date.

Study day will appear in any listings where an assessment date or event date appears.

In case of partial or missing event date, study day will appear missing while any associated durations will be presented based on the imputations described in appendix A3.

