##### 5.8.2.1 *Total Duration of Treatment*

Total duration of treatment is defined as (last dose date of IMP administration of palovarotene in Study CLIN-60120-452 - first dose date of IMP administration of palovarotene in Study CLIN-60120-452 + 1). The first dose date will be the start date of the first record in eCRF Dosing Form and the last dose date will be the date of last contact.

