#### *Algorithm for TEAE*

The date imputation algorithm for incomplete adverse event start dates is described in the table below. Classification of adverse event according to its treatment-emergent status is then done using the imputed date.

In the following table, all dates are presented using an YYYY-MM-DD format. As an example, suppose First IMP administration = 2002-08-11 and several AEs have incomplete start dates.

Description of incomplete date	Imputed numeric date	Example	
		Character date	Imputed date
Day is missing			
YYYY-MM < YYYY-MM of [First IMP admin.]	YYYY-MM-01	2002-07-XX	2002-07-01
YYYY-MM = YYYY-MM of [First IMP admin.]	Min ([First IMP admin.], AE end date)	2002-08-XX	Min (2002-08-11, AE end date)
YYYY-MM > YYYY-MM of [First IMP admin.]	YYYY-MM-01	2002-09-XX	2002-09-01
Day and month are missing			
YYYY < YYYY OF [First IMP admin.]	YYYY-01-01	2001-XX-XX	2001-01-01
YYYY = YYYY OF [First IMP admin.]	Min ([First IMP admin.], AE end date)	2002-XX-XX	Min (2002-08-11, AE end date)

YYYY > YYYY OF [First IMP admin.]	YYYY-01-01	2003-XX-XX	2003-01-01
Day, month, and year are missing			
XXXX-XX-XX	Min ([First IMP admin.], AE end date)		Min (2002-08-11, AE end date)

YYYY = non-missing year, MM = non-missing month, DD = non-missing day, XX = missing field.

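### Dose at AE onset is taken only from dosing records before the AE date, so Day-1 TEAEs (including those imputed to Day 1) get no dose and dose-change-day onsets get the old dose

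*SAP*

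**What the plan says.** **TEAE rule (SAP 5.7.2.2).** An AE is treatment-emergent under the rule "Events with start date on or after the date of first IMP administration and up to 30 days after date of last dose". Day 1 is therefore included.

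**Dose-at-onset rule (SAP 5.7.2.2).** AE start dates are merged with the dosing log. The log holds no end dates, so "the latest dosing record prior to the AE start date will be identified". One fallback is given: "If the dosing record is either 0 mg or after treatment discontinuation the regimen will be set to" off treatment. Nothing is said about an AE for which no record is found.

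**Tables that use it.** "The below summaries will also be provided by treatment dose at time of AE onset (5mg, 10/20mg and all palovarotene"). Six summaries follow, and the section on deaths and SAEs adds a seventh, for serious TEAEs.

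**Dates.** SAP 5.1.4: "Reference start date is defined as the day of the first IMP administration of palovarotene (Day 1) in Study CLIN-60120-452". SAP 5.8.2.1: "The first dose date will be the start date of the first record in eCRF Dosing Form".

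**Imputation (SAP Appendix A3).** The AE start becomes "Min ([First IMP admin.], AE end date") in three cases: the day is missing in the first-dose month, day and month are missing in the first-dose year, or the whole date is missing.

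**Exposure (SAP 5.8.2).** Each dosing period ends the day before the next one starts, so a change day belongs to the new dose.

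**The concern.** The TEAE rule and the dose rule treat the boundary day differently. The TEAE rule includes the first dosing day. The dose rule needs a record dated earlier than the event, and this study's log has none before Day 1. Appendix A3 also sends a whole class of incompletely dated events to that day, so the gap is more than the occasional true Day-1 onset.

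The same strict inequality conflicts with the exposure rule on every dose-change day. AE attribution and exposure come from the same form but would disagree about which dose applied.

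At stake are the seven summaries by dose at onset. They are the SAP's only AE tables that place each event at the dose in force when it began; the regimen columns group participants instead. Protocol 6.1 lets participants transition while on flare-up treatment, so a lost Day-1 event could belong to either dose column.

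**Working it through.** The plan gives no figure to reproduce, so the check applies the rules to dates.

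**Inputs from the SAP.** First dose 2002-08-11 (the Appendix A3 example); the TEAE, imputation, dose-at-onset and exposure rules above.

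**Assumed for illustration.** Dosing records of 5 mg from 2002-08-11, 20 mg from 2002-10-01, 10 mg from 2002-10-29 (28 days later) and 5 mg from 2002-12-24 (56 days later); last dose 2003-02-28.

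**Rules compared.**
- As written: latest record with record date < AE date.
- Alternative: latest record with record date ≤ AE date.
- Exposure (SAP 5.8.2): the period from each start date to the next start date minus 1.

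| AE start as recorded | Date used | As written | On or before | Exposure period |
|---|---|---|---|---|
| 2002-08-11 (Day 1) | 2002-08-11 | no record | 5 mg | 5 mg |
| 2002-08-XX, 2002-XX-XX or fully missing, no earlier end date | 2002-08-11 | no record | 5 mg | 5 mg |
| 2002-08-12 (Day 2) | 2002-08-12 | 5 mg | 5 mg | 5 mg |
| 2002-10-01 (20 mg starts) | 2002-10-01 | 5 mg | 20 mg | 20 mg |
| 2002-10-29 (10 mg starts) | 2002-10-29 | 20 mg | 10 mg | 10 mg |
| 2002-12-24 (return to 5 mg) | 2002-12-24 | 10 mg | 5 mg | 5 mg |

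An AE recorded as 2002-08-XX that ended on 2002-08-05 is imputed to 2002-08-05. It is not a TEAE and is not part of the problem.

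**Day count.** Exposure is 51 + 28 + 56 + 67 = 202 days (5, 20, 10 and 5 mg periods). As written, 1 day has no dose and 3 days carry the old dose: 4/202 = 2.0%. The 20-to-10 mg step stays within the 10/20 mg column, so 3 days (Day 1, escalation, return to 5 mg) affect a column: 3/202 = 1.5%. With *on or before*, all 202 days agree with the exposure periods.

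These are shares of days, not of events. Imputation concentrates events on Day 1, so the share of events could be larger.

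**The case against.** **Prior to may be loose drafting.** SAP 6.1 labels the baseline window as up to and including Day 1 while describing it as before first dosing. But SAP 5.5 separates *before* from *on or after*, and the TEAE rule includes the boundary day explicitly. A programmer following the dose rule would code a strict inequality.

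**A fallback may exist.** SAP 5.1.1.2 sends unavailable regimens to case-by-case discussion. That clause concerns the participant's regimen group, not the dose at an event.

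**Imputed dates may not apply.** The TEAE algorithm in Appendix A3 names only treatment-emergent status as its use. The appendix's opening covers any assignment based on dates. If imputation were excluded, a partial date could not be merged and the dose would still be undefined.

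**The old dose is sometimes right.** This stands. Protocol 6.5 and 7.1.3 provide for reduction or interruption because of intolerable reactions. If an AE prompts a same-day change, *on or before* alone would attribute it to the reduced dose or to off treatment.

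A reader might also infer more than the documents support:
- *Worsened parent-study AEs also lose their dose.* SAP 5.7.2.2 detects worsening by comparing new AEs in this study with the ongoing ones, so the worsened event can be expected to carry its own later start date.
- *Events shift one way, from higher to lower dose.* Escalation and return to 5 mg shift events in opposite directions.
- *The rule is why columns fail to add up.* Participant counts need not sum under any wording, since one person can have events at both doses. Off-treatment events and the reduced doses in protocol Table 5 (15, 12.5, 7.5, 2.5 and 1 mg) also have no labelled column.
- *The tables by dose at onset are the only link between AEs and dosing.* All AE tables are also split by regimen, though that is not dose at onset.

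**Conclusion.** The point holds in a limited form. As written, Day-1 TEAEs and those imputed to Day 1 have no dose and leave the 5 mg and 10/20 mg columns. Whether they remain under all palovarotene is not stated. Onsets on change days are attributed against the SAP's own exposure periods, in both directions.

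Overall TEAE incidence, the primary endpoint, is unaffected, and the study is descriptive. The number of affected events depends on how many AEs have Day-1, partial or change-day dates, which the documents do not give. The conclusion assumes that *prior to* is programmed literally and that only this study's dosing form is used, as SAP 5.1.1.2 indicates for regimen. It deserves correction before database lock because the stated rule, followed faithfully, misplaces events.

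**What to change.** 1. In SAP 5.7.2.2, identify the latest dosing record on or before the AE start date, using the Appendix A3 imputed date where the recorded date is partial or missing. This matches the TEAE rule and the SAP 5.8.2 periods.
2. Add a tie rule: an AE recorded as leading to a same-day dose reduction or interruption is attributed to the dose in force before the change. State whether this extends to AEs leading to a dose increase, since the SAP tabulates changes in both directions.
3. Reconcile on event counts only: TEAEs in the 5 mg and 10/20 mg columns, plus those at any other dose, plus off treatment, should equal total TEAEs. Show any event still without a record as its own row.

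The cost is small: a revised sentence, a tie rule that needs the AE action-taken field (assumed available, since TEAEs leading to dose change are tabulated) and a little programming. No new data collection is expected. Events under the tie rule will differ from the exposure periods by design, which a footnote should say.
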